12. MONITORING, AUDIT & INSPECTION

12.1. Monitoring

A trial risk assessment will be carried out by the Sponsor prior to Sponsorship approval being granted. The Sponsor will determine the appropriate extent and nature of monitoring for the trial and will delegate monitoring to appropriately qualified and trained monitors. A Monitoring Plan will be developed by the Sponsor based on the trial risk assessment which will include on site and/or remote monitoring. The Monitoring Plan will be reviewed regularly using a risk-based approach and updated as required. The Monitoring Plan will detail the

procedures and anticipated frequency of monitoring and processes reviewed. Sites must have access to source data for purposes of remote monitoring and assist the Sponsor in monitoring of the trial. In recognition that source data may come from different sources at each site, sites shall ensure that a source data identification list is supplied to the Monitoring Team in advance of any monitoring review and ensure this data is available on the agreed date and time to facilitate the review.

13. ETHICAL AND REGULATORY CONSIDERATIONS

13.1. Research Ethics Committee (REC) review & reports

Before the start of the trial, approval will be sought from an independent REC for the trial Protocol, Informed Consent Form, and other relevant documents.

Substantial amendments that require review by REC will not be implemented until the REC grants a favourable opinion for the trial.

All correspondence with the REC will be retained in the TMF.

A progress reports will be submitted to the REC according to REC approval conditions. It is the CI's responsibility to produce the REC reports as required.

The CI will notify the REC of the end of the trial. If the trial is ended prematurely, the CI will notify the REC, including the reasons for the premature termination. The CI will submit a final report with the results, including any publications/abstracts, according to REC approval conditions.

A copy of all REC reports will be submitted to the Sponsor.

13.2. Peer review

This trial has been funded by LifeArc who have reviewed the grant application. The trial has also been peer reviewed by EMBARC. The protocol has been reviewed and approved by the Sponsor Committee.

Resulting publications will be reviewed by the referees of the journal to which the paper will be submitted.

13.3. Public and Patient Involvement

Input from patients will be incorporated into each phase of the project through engagement with the European Lung Foundation patient advisory group, part of EMBARC.

Patient representatives will be incorporated into the trial steering committee, the TMG and will advise on all aspects of study design, implementation and dissemination. The patient advisory group has been operating since 2015 and is a group of international bronchiectasis patients supported by the European Lung Foundation and inputs into clinical research across the EMBARC programme.

The patient representatives have given input into the participant facing documents and aspects of trial design relating to trial participation and burden.

13.4. Regulatory Compliance

The trial will not commence until a Clinical Trial Authorisation is obtained from the MHRA and favourable REC opinion. The protocol and trial conduct will comply with the Medicines for Human Use (Clinical Trials) Regulations 2004 and any relevant amendments.

Before any site can enrol participants into the trial, the CI, PI, or delegate will ensure that appropriate approvals from participating organisations are in place.

For any amendment to the trial, the CI, PI, or delegate, in agreement with the sponsor, will submit information to the appropriate body for them to review and issue approval for the amendment. The CI, PI or delegate will work with sites so they can put the necessary approvals and arrangements in place to implement the amendment to confirm their support for the trial as amended.

13.5. Protocol compliance

Prospective, planned deviations or waivers to the protocol are not allowed, e.g., it is not acceptable to enrol a participant if they do not meet the eligibility criteria or restrictions specified in the trial protocol. Trial staff will not implement deviations to the protocol except where necessary to eliminate an immediate hazard to trial participants.

Accidental protocol breaches can happen at any time. They will be adequately documented on the relevant forms and reported to the CI and Sponsor using the TASC Breach Reporting Form. If there is a breach of the protocol, the nature of and reasons for the breach will be documented in the trial Breach Log. Breaches from the protocol which are found to frequently recur are not acceptable, will require immediate action and could potentially be classified as a serious breach.

13.6. Notification of Serious Breaches to GCP and/or the protocol

A “serious breach” is a breach which is likely to affect to a significant degree –

- a) the safety or physical or mental integrity of the participants of the trial; or
- b) the scientific value of the trial

The sponsor will be notified immediately of any case where the above definition applies during the trial conduct phase. The sponsor of a clinical trial will notify the licensing authority in writing of any serious breach of

- a) the conditions and principles of GCP in connection with that trial; or
- b) the protocol relating to that trial, as amended from time to time.

If a serious breach of the protocol or GCP is suspected, this will be reported to the Sponsor immediately using the Breach Reporting Form and will be recorded in the eCRF and documented in the trial Breach Log.

If a breach necessitates a subsequent protocol amendment, this will be submitted as per section 13.10.

13.7. Data protection and participant confidentiality

The CI and trial staff will comply with the requirements of GDPR and the UK Data Protection Act 2018 or any subsequent amendment or replacement thereof with regard to the

collection, storage, processing and disclosure of personal data and will uphold the principles of GDPR in Article 5.

The CI and trial staff will also adhere to the NHS Scotland Code of Practice on Protecting Participant Confidentiality or local equivalent.

All trial records and data will be managed in a manner designed to maintain participant confidentiality. All records, electronic or paper, will be kept in a secure storage area with access limited to appropriate trial staff only. Computers used to collate data will have limited access measures via usernames and passwords. Age, gender, and ethnicity will be the only personal identifiable details held on Castor EDC system. Date of Birth will be held on the TRuST system to allow for the identification of participants where emergency unblinding is required.

Personal data or data concerning health will not be released without the existence of a legal basis for processing under Articles 6 and 9 of GDPR, such as official authority 6(1)e or substantial public interest 9(2)g. The CI and trial staff will not disclose or use for any purpose other than performance of the trial, any data, record, or other unpublished, confidential information disclosed to those individuals for the purpose of the trial. Prior written agreement from the Sponsor will be required for the disclosure of any said confidential information to other parties.

Access to collated participant data will be restricted to the CI and appropriate delegated trial staff. In the event that data are shared with collaborators or groups wishing to undertake further analysis, collaborators will not have access to personal identifiable details other than those held on the EDC system. Pseudonymised participant data will also be available to interested parties after publication of the final report upon reasonable written request to the CI and subsequent approval.

The transfer of data to collaborators or for use in further research will be as described in the Clinical Research Agreement.

Published results will not contain any personal data that could allow identification of individual participants.

13.8. Financial and other competing interests for the Chief Investigator, PIs at each site and committee members for the overall trial management

The CI has worked as an advisory to the funder, LifeArc.

Additional disclosure information, if any, will be collected at site initiation and documented in the site file. Members of the TSC and DMC will complete a competing interest form, which will be held in the TMF

13.9. Indemnity

The UoD and Tayside Health Board are Co-Sponsoring the trial.

Insurance. – The UoD will obtain and hold Clinical Trials indemnity cover for legal liabilities arising from the trial.

Tayside Health Board will maintain its membership of the Clinical Negligence and Other Risks Insurance Scheme (CNORIS) which covers the legal liability of Tayside in relation to the trial.

Where the trial involves UoD staff undertaking clinical research on NHS participants, such staff will hold honorary contracts with Tayside Health Board which means they will have cover under Tayside's membership of the CNORIS scheme.

Indemnity. The Co-Sponsors do not provide trial participants with indemnity in relation to participation in the Trial but have insurance for legal liability as described above.

Where other Scottish Health Boards are participating as trial sites, those other Scottish Health Boards will maintain membership of CNORIS to cover their liability in relation to their conduct of the trial.

Other participating sites will maintain membership of a scheme similar to CNORIS.

13.10. Amendments

The closing of treatment arms and the addition of new treatment arms will require an amendment to the protocol.

Amendments to the protocol will be conducted in compliance with Sponsor Standard Operating Procedures. The decision to amend the protocol will lie with the CI after consultation with the TMG, and trial statistician. The TSC will also be consulted on any major amendments. The CI will seek Sponsor approval for any amendments to the Protocol or other approved trial documents. The Sponsor will decide whether an amendment is substantial or non-substantial. The CI will be responsible for submitting the amendment to the appropriate regulatory authorities and communicating amendments to sites.

Amendments to the protocol or other trial documents will not be implemented without approval from the Sponsor and subsequent approval from the appropriate REC and/or MHRA, as appropriate, and appropriate site approvals. The amendment history will be detailed in an Amendment Log.

13.11. Post trial care

Following the end of trial, participants should be continued, started, or restarted on the appropriate treatment for their bronchiectasis. No provision for continuation of trial drug will be made by the trial team or Sponsor.

13.12. Access to the final trial dataset

The CI and Trial Statistician will have access to the final trial dataset. Access to the final trial dataset to others will be approved by the CI. See also section 13.7.

14. DISSEMINATION POLICY

Details of the trial and clinical trial final report will be published on ISCTRN Registry, no later than 12 months after the end of trial. Trial results will be available to the public via the ISCTRN registry. The report will be made available to the Funder. The report can be used for publication and presentation at scientific meetings. Trial investigators have the right to publish orally or in writing the results of the trial. The participant representatives will be invited to suggest further dissemination activities for patients.

Participants in the trial will be notified of the results via a Results Letter.

14.1. Authorship eligibility guidelines and any intended use of professional writers

The data arising from this trial resides with the trial team and ownership with the UoD. On completion of the trial, the trial data will be analysed and tabulated, and a clinical trial final report will be prepared.

Authorship and the publication will be defined and developed by the TSC and the site investigators. An inclusive approach will be taken with either named or group authorship (e.g., “on behalf the AIR-NET Investigators”). In the case of group authorship all contributing participants will be named in (for example) a supplementary appendix. Named authors will be expected to meet authorship criteria set out by the International Committee of Medical Journal Editors.

16. APPENDICIES

16.1. Appendix 1-Risk

Risks associated with trial interventions
 
 A ≡ Comparable to the risk of standard medical care
 
 B ≡ Somewhat higher than the risk of standard medical care
 
 C ≡ Markedly higher than the risk of standard medical care

Justification:
 
These repurposed therapeutics have established real-world evidence based on their safety profile, side effects, pharmacokinetics and pharmacodynamics, drug–drug interactions, and experience in different patient populations.

Outline any other processes that have been put in place to mitigate risks to participant safety (e.g. DMC, independent data review, etc.)
 
There will be an early review of safety and treatment compliance data by the DMC in each treatment arm. This will take place after the 10th randomised participant to the treatment arm has reached 28 days post-randomisation. Based on this review, the DMC will make recommendations to the TSC as to whether recruitment to the treatment arm should stop, continue as planned, or whether any modifications should be considered (e.g. dosing).

Outline any processes (e.g. IMP labelling +/- accountability +/- trial specific temperature monitoring) that have been simplified based on the risk adapted approach.
 
Nil

Potential or identified risk of clinical significance	Summary of data/rationale for risk	Mitigation Strategy
Doxycycline		
Photosensitivity	
Photosensitivity erythematous rash was observed in individuals undergoing doxycycline for infection treatment or malarial prophylaxis and tends to resolve upon discontinuation. This is thought to be due to ultraviolet (UV)-A radiation, mediated by mitochondrial toxicity and oxidative stress. Individuals with lighter complexion or on higher doses may be more prone to photosensitivity. Incidence for photosensitivity is highly
	
-Participants randomised to the doxycycline arm are advised to avoid sun exposure, wear protective clothing and use broad spectrum sunscreen (against UV-A and UV-B radiation)

	variable depending on location and population, ranging between 7.3-21.2% of individuals. (Tan et al. 2011).	
Gastrointestinal Disorder	People on doxycycline commonly experience gastrointestinal symptoms which are generally mild to moderate, including nausea, abdominal pain, vomiting, and diarrhoea. Doxycycline may also cause oesophageal inflammation or ulcers. It is considered that long oesophageal transit time and dehydration contributes to nausea and mucosal inflammation related to doxycycline. (Tan et al. 2011).	- Participants are advised to ingest the pill in an upright position, with plenty of fluid, and avoid taking before bedtime.
Disulfiram 400mg		
Disulfiram-Ethanol Reaction	Disulfiram-Ethanol Reaction (DER) mostly occurs in the first 12 hours after administration. Although severity of the DER is related to the disulfiram dose and ethanol intake, it was also seen in cases with blood alcohol as low as 10mg/100ml. A study found 19% of patients on disulfiram experienced DER while using alcohol-based hand sanitizer. (Lanz et al. 2023).	- Participants randomised to Disulfiram will be advised to abstain from alcoholic beverages or the use of any alcohol-based products during intervention - Proper ventilation during administration may alleviate DER when using alcohol based hand sanitizer
Hepatotoxicity	Carbon disulfide is released during hepatic disulfiram metabolism, and can cause hepatocellular degeneration or necrosis. Hepatotoxicity have previously manifested in the form of asymptomatic transaminitis to rare fulminant hepatic failure. This may be attributed to pre-existing alcoholic liver condition, but also found in 25% patients with	- Regular clinical and laboratory monitoring for hepatotoxicity

	no previous alcohol misuse. Most of these effects are reversible when Disulfiram is stopped. (Lanz et al. 2023).	
Dipyridamole		
Headache	
Headaches are a well-known transient side effects of dipyridamole, due to its vasodilatory properties. This often leads to discontinuation, as seen in 8% of patients who were enrolled into the dipyridamole arm in the Second European Stroke Prevention (ESPS2) Trial.
 
A bioequivalence trial comparing two different formulations of dipyridamole involving mostly young healthy adults found that 72% of volunteers reported at least one episode of headache over the course of two weeks. This bioequivalence trial also found that the volunteers are more likely to experience headache in the first week, 2-3 hours after the morning dose, and all volunteers recovered fully from the headaches regardless of severity. (Theis, Deichsel, and Marshall 1999)
	- Participants should be informed that they may experience transient headaches while initiating dipyridamole, and reassurance that it will improve with time.
Bleeding	
As an antiplatelet, patients may be at a higher risk of bleeding complications. Adding dipyridamole to anticoagulation increases the risk of bleeding by about 50% (Massel and Little 2013).
 
However, for patients not on anticoagulation, this risk was not seen in the large clinical trials performed in patients who had a Stroke or Transient Ischaemic Attack (TIA). In
	
- Participants who are on dual antiplatelet, any anticoagulant, or any coagulopathy should not be randomised to dipyridamole. Participants who are already on Aspirin are safe to be recruited.
 
- Participants who recently had any gastrointestinal bleeding, head trauma, or major operation within 30 days should not be randomised to dipyridamole

	ESPS2, patients who were randomised to placebo (n=1649) and dipyridamole alone (n=1654) reported similar events for bleeding any site, 74 and 77 respectively. ESPS2 also found that the bleeding risk between Aspirin (n=1649) and Aspirin plus Dipyridamole (n=1650) are similar at 135 and 144 events respectively (Diener et al. 1996).	
Hypotension	Dipyridamole is a potent vasodilator and the intravenous form was used in cardiac investigations. Oral dipyridamole is unlikely to induce hypotension, and was well tolerated even in patients with Escherichia coli endotoxin induced endotoxemia. It remains a theoretical risk and should be used with caution (Ramakers et al. 2011).	- Participants with severe coronary artery disease, recent myocardial infarct, or left ventricular systolic dysfunction can be recruited if their condition is stable.
Neutrophilic Inflammation Attenuation		
Infection	Theoretically, neutrophilic inflammation attenuation may increase the number of infections. This is however not commonly observed in clinical trials that used either disulfiram, dipyridamole or doxycycline in 1 month. The perceived risk is small.	- Regular clinical and laboratory monitoring for infection - An independent DMC is in place to periodically evaluate clinical trial safety data.

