2.1. Assessment and Management of Risk

This trial is categorised as: Type B = Somewhat higher than the risk of standard medical care

The trial treatments are all repurposed drugs already approved for use in conditions other than bronchiectasis.

Arm 1: Usual care

Arm 2: Disulfiram

Disulfiram is an alcohol deterrent compound licensed for use as an adjuvant in the treatment of drinking problems. The most common adverse reaction (AR) reported during treatment is alcohol reaction. Disulfiram–ethanol reactions often develop within 15 minutes after exposure to ethanol; symptoms usually peak within 30 minutes to 1 hour, and then gradually subside over the next few hours. Symptoms may be severe and life-threatening. Participants will be informed of the reaction risk and must agree to abstain from alcohol during treatment and for up to 14 days after discontinuation.

Arm 3: Dipyridamole

Dipyridamole is licensed for use in secondary prevention of ischaemic stroke and transient ischaemic attacks and as an adjunct to oral anti-coagulation for prophylaxis of thromboembolism associated with prosthetic heart valves. The most commonly reported adverse effects are headache, dizziness, diarrhoea, nausea (very common, $\geq 1/10$) and angina pectoris, vomiting, rash, myalgia (common, $\geq 1/100 < 1/10$).

Arm 4: Doxycycline

Doxycycline is licensed for use in the treatment of a variety of infections caused by susceptible strains of Gram-positive and Gram-negative bacteria and certain other micro-organisms. The most common adverse effects observed in patients receiving tetracyclines, including doxycycline, are hypersensitivity, headache, nausea/vomiting, photosensitivity reaction rash including maculopapular and erythematous rashes (common, $\geq 1/100 < 1/10$).

Management of risk is described in Appendix 1. However, this is the first use of these medications in this patient population, hence there is the *possibility* of additional unknown risks.

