6.3. Open treatment arm specific exclusion criteria

6.3.1. Arm 2: Disulfiram

- Currently on Disulfiram (patients should have a washout period of at least 30 days from last dose if they have previously received this medication)
- Hypersensitivity to Disulfiram
- Participant, or investigator objects to randomisation to Disulfiram
- Does not agree to cease consumption of alcohol during intervention and for 14 days following treatment discontinuation
- Chronic liver disease
- Alanine transaminase (ALT)>135 U/L at screening,
- Bilirubin >30 umol/L at screening.
- Uncompensated cardiac failure
- Coronary artery disease (diagnosis of stable or unstable angina, previous myocardial infarction)
- Previous history of stroke or transient ischaemic attack
- Uncontrolled hypertension
- Hereditary problems of galactose intolerance, total lactase deficiency or glucose-galactose malabsorption
- Recent psychiatric exacerbation
- Any significant acute or chronic psychiatric condition, including severe personality disorder, psychotic disorder or suicide risk.
- Hypothyroidism
- Porphyria

- Diabetes Mellitus
- Epilepsy

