8.11. Trial restrictions

	Treatment	Trial restrictions
All arms		To avoid contamination between the arms, participants who develop an exacerbation during the study and require antibiotic treatment should receive an antibiotic other than doxycycline. If participants are not able to safely avoid doxycycline during the trial period they should not be enrolled in the study.
Arm 2	Disulfiram	Alcohol Participants will be required to consent to not consuming alcohol for duration of treatment and at least 14 days after stopping treatment. Written advice will be provided to participants about how to avoid products containing alcohol during the trial period.
Arm 3	Dipyridamole	Participants should not commence new oral anticoagulant drugs during the trial period. Participants needing to initiate anticoagulants should withdraw from the study.
Arm 4:	Doxycycline	No restrictions. Exacerbations of bronchiectasis should be treated with an alternative antibiotic.
All	Nasal brushing	Participants should not have a nasal brushing performed if they are receiving anticoagulants (oral anticoagulants or warfarin) or have a history of deviated nasal septum, base of skull fracture or severe epistaxis. If any of these are present the nasal brushing will be omitted. This will not affect their participation in the trial.

WOCBP must be willing to have pregnancy testing prior to trial entry and at each research visit, unless the participant has been randomised to usual care.

A woman is considered of childbearing potential, i.e. fertile, following menarche and until becoming post-menopausal unless permanently sterile. A post-menopausal state is defined as no menses for 12 months without an alternative medical cause (including use of hormone replacement therapy).

In addition, WOCBP must be willing to use a form of a medically approved birth control method throughout the trial (and for minimum of 4 weeks after last dose), unless randomised to usual care, which include:

- combined (estrogen and progestogen containing) hormonal contraception associated with inhibition of ovulation:
 - oral
 - intravaginal
 - transdermal
- progestogen-only hormonal contraception associated with inhibition of ovulation:
 - oral
 - injectable
 - implantable
- intrauterine device (IUD)
- intrauterine hormone-releasing system (IUS)

- bilateral tubal occlusion
- vasectomised partner

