9.4. Reference Safety Information, open treatment arms

The current version, of the RSI will be held in the TMF - specifically in Pharmacy Site File, Investigator Site File (ISF) and Sponsor File. The RSI will be reviewed at least annually and where there have been any changes to the Reference Safety Information which may impact on the trial the protocol will be reviewed and a substantial amendment submitted for regulatory approvals.

	Treatment	Reference Safety Information
Arm 2	Disulfiram	Summary of Product Characteristics, Section 4.8
Arm 3	Dipyridamole	Summary of Product Characteristics, Section 4.8
Arm 4:	Doxycycline	Summary of Product Characteristics, Section 4.8

Mitigation of risks is detailed in Appendix 1.

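### The disulfiram alcohol rules start only with treatment: nothing in the protocol requires a question about recent drinking, or a delay, before a first dose dispensed at the randomisation visit

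*Protocol*

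**What the plan says.** Four places in the protocol set the alcohol rules for Arm 2.

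- Section 2.1 warns of the reaction ("Symptoms may be severe and life-threatening"). It says participants must agree to abstain during treatment and for up to 14 days after stopping.
- Section 6.3.1 excludes from the arm anyone who "Does not agree to cease consumption of alcohol during intervention and for 14 days following treatment discontinuation".
- Section 8.11 states: "Participants will be required to consent to not consuming alcohol for duration of treatment and at least 14 days after stopping treatment". It adds: "Written advice will be provided to participants about how to avoid products containing alcohol during the trial period".
- Appendix 1 (16.1), under the disulfiram-ethanol reaction, states: "Participants randomised to Disulfiram will be advised to abstain from alcoholic beverages or the use of any alcohol-based products during intervention".

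Appendix 1 also describes the hazard. The reaction "mostly occurs in the first 12 hours after administration", and cases occurred at blood alcohol as low as 10 mg/100 ml. Sections 2.1 and 9.4 both send the reader there: "Management of risk is described in Appendix 1" and "Mitigation of risks is detailed in Appendix 1".

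On timing, section 7.1.2 has eligibility assessed at visit 2 once all results have been reviewed. The schedule in Appendix 4 puts randomisation and dispensing at that same visit, day 0.

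**The concern.** The protocol takes care over alcohol after disulfiram but has no rule on alcohol before it. Participants first learn that they are allocated to disulfiram on the day they receive the drug. Until then they have only agreed to stop drinking if and when treatment starts. Someone who drank the evening before visit 2, or that morning, has broken no rule, and nobody is required to ask.

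What is at stake is the safety of the first dose. The reaction is one the protocol regards as potentially life-threatening and, in Appendix 1, as related in severity to the disulfiram dose. The dose here is 400 mg daily, twice the 200 mg maximum that section 2 attributes to the product's own labelling.

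A smaller matter sits alongside. Appendix 1, which two sections name as the home of risk mitigation, stops its advice at the end of the intervention and omits the following 14 days.

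**Working it through.** The protocol gives no figure to reproduce. The check is a comparison of texts, with a little arithmetic.

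**1. When each alcohol rule starts and ends (28-day course)**

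| Place | Starts | Ends |
|---|---|---|
| 2.1 | treatment | up to 14 days after stopping |
| 6.3.1 | intervention | 14 days after stopping (28 + 14 = day 42) |
| 8.11, drinking | treatment | at least 14 days after stopping (day 42 or later) |
| 8.11, product advice | trial period | trial period |
| Appendix 1 | intervention | end of intervention (day 28) |

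No drinking rule starts before treatment. The product advice in 8.11 is an Arm 2 provision, so it applies once allocation is known, and it concerns products containing alcohol. It sets no pre-dose interval.

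**2. Other places where a pre-dose rule could sit**

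- Section 6.3.3 lists alcohol dependence as an exclusion for doxycycline only.
- Section 8.9 lists alcohol as an interaction but sets no interval.
- Section 7.7 limits the medical history to chronic conditions tied to eligibility and to medication allergies.
- Appendix 4 contains no alcohol question at any visit.

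None of these requires a question about recent drinking or a delayed first dose.

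**3. How long an interval might be needed**

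The documents give no elimination rate, so no interval can be derived from them. As an assumption, take elimination of 10 to 20 mg/100 ml per hour and a starting level of 50 to 200 mg/100 ml.

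- Hours to 10 mg/100 ml = (start − 10) / rate
- Hours to zero = start / rate

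| Start (mg/100 ml) | Rate (mg/100 ml per hour) | Hours to 10 mg/100 ml | Hours to zero |
|---|---|---|---|
| 50 | 10 | 40/10 = 4.0 | 50/10 = 5.0 |
| 50 | 20 | 40/20 = 2.0 | 50/20 = 2.5 |
| 200 | 10 | 190/10 = 19.0 | 200/10 = 20.0 |
| 200 | 20 | 190/20 = 9.5 | 200/20 = 10.0 |

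Across that range, alcohol falls to the lowest level at which Appendix 1 reports a reaction in 2 to 19 hours, and to zero in 2.5 to 20 hours. A 24-hour interval would cover the whole assumed range.

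**4. What a delay costs**

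Starting one day late leaves 27 of 28 days of exposure before the day 28 sputum sample: 1/28 = 3.6% less for those affected. Appendix 4 already accepts visits up to 2 days late, so the shift is within the tolerance the protocol allows.

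**5. The Appendix 1 period**

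The drinking rule covers 28 + 14 = 42 days and the Appendix 1 text covers 28. The difference is 42 − 28 = 14 days, which is 33% of the rule's length. It counts days missing from one table entry and does not measure unprotected time, because 6.3.1 and 8.11 cover all 42 days.

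**The case against.** **On the first dose.** An investigator may object to randomising a participant to disulfiram under 6.3.1, and section 7.3.1 requires eligibility for each arm to be assessed before randomisation. An investigator who knows of recent drinking can therefore withhold the arm. Section 2.1 has participants told of the reaction risk, and agreement on alcohol precedes allocation, so being allocated is not their first warning. Dispensing on day 0 does not mean dosing on day 0, because the hour of the first dose is not fixed. The information sheet, the written alcohol advice and the pharmacy manual are not shown and may say when to start.

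All of this is fair, and it keeps the point small. It does not supply the missing rule: discretion works only if someone asks, and nothing in the protocol makes anyone ask.

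**On the period after treatment.** A reader might infer from Appendix 1 that drinking is allowed once treatment ends, or that staff would be led to stop their advice 14 days early. The documents do not support that. Appendix 1 is silent on the later period and does not permit drinking. Sections 6.3.1 and 8.11 bind every participant in the arm for the 14 days, and section 2.1 mentions a period after stopping before it refers the reader to Appendix 1.

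**On alcohol-based products.** A reader might also infer that nothing covers these after treatment. Yet the product advice in 8.11 runs for the trial period. Section 7.3 equates completing 56 days of follow-up with the end of trial, and the last scheduled visit is day 56. The advice can therefore be read as lasting to day 56, beyond day 42, and that criticism falls away.

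**Conclusion.** The point holds in a limited form. As written, the protocol requires at least 14 alcohol-free days after the last dose of disulfiram and none before the first, although the drug is handed over at the randomisation visit and the reaction is described as possibly life-threatening. A question at visit 2 and a short delay where needed would close the gap.

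This rests on two conditions. The first is that the unseen participant and pharmacy materials do not already impose such a rule; if they do, the protocol should still state it. The second is that the Appendix 1 statements on timing and blood alcohol apply to a first dose taken after drinking. The protocol does not discuss that sequence separately.

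A reader might take 24 hours to be a threshold set by the documents. It is not: it rests on assumed elimination rates and starting levels, and the choice belongs to the sponsor.

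The Appendix 1 omission is a wording alignment only. Neither part affects the analysis method or the error rates. The priority is low and the confidence medium.

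**What to change.** 1. **Section 8.11, Arm 2 (main change).** Add: *At visit 2, staff ask about and record recent alcohol intake. The first dose is not taken until an alcohol-free interval set by the sponsor has passed.* A suggested value is 24 hours, on the assumptions shown above.
2. **Appendix 1, disulfiram-ethanol reaction (secondary alignment).** Replace the words limiting the advice to the intervention with: *during treatment and for at least 14 days after the last dose*.
3. **Leave the product advice in 8.11 as it is.** Replacing the trial period there with a 14-day minimum could shorten that advice from day 56 to day 42.

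The cost is one recorded question at an existing visit and one wording change, with no extra visit. A few disulfiram participants may start up to about a day later and have 27 instead of 28 days of exposure before the primary sample (3.6% less, in that arm only).
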